#### 2. Secondary Outcomes

##### a. Miscarriage

- i. We will use diagnosis codes and documentation within clinical notes to subsequently identify miscarriages that present to the health care setting.

##### b. Abortion

- i. We will also identify procedural abortions and prescriptions for medical abortions. Using documentation within clinical notes to distinguish between miscarriage-related abortions (i.e., those performed after early pregnancy loss, incomplete abortions, and ectopic pregnancies) and induced abortions, this outcome will focus specifically on induced abortions.

##### c. Prenatal vitamin prescriptions prior to pregnancy

- i. To characterize family planning among participants, we will assess new use of prenatal vitamins, including multivitamins. Physicians can prescribe these vitamins or document over-the-counter use of them in

the electronic health record. We will exclude those that were prescribed or documented during pregnancy and focus specifically on those that occurred prior to any pregnancy over the 10 months of the trial.

- d. Contraception
  - i. To further understand family planning among participants, we will assess utilization of long-acting reversible contraceptive methods (intrauterine devices or implants) and prescriptions for hormonal birth control methods (pill, patch, ring).
- e. Number and timing of prenatal visits before delivery
  - i. In addition to quantity of visits, we will also assess for initiation during the first trimester and calculate the Adequacy of Prenatal Care Utilization (APNCU) Index, which characterizes the adequacy of a patient's prenatal care as inadequate, intermediate, adequate, or adequate plus based on the timing of their prenatal care initiation and the number of prenatal visits after initiation.
- f. Composite of birth outcomes
  - i. Following McConnell et al. (2022), we will construct a composite of at least one of: low birth weight, preterm birth, small for gestational age, or perinatal mortality. These are described in further detail below.
  - ii. *Birth weight* is a continuous measure of the infant's birth weight in grams. *Low birth weight* is defined as a birth weight less than 2500 grams.
  - iii. *Gestational age* at birth is a continuous measure of the infant's gestational age at birth. *Preterm birth* is defined as an infant born before a gestational age of 37 weeks.
  - iv. *Birth weight for gestational age* is a continuous measure of the infant's birth weight relative to the average in the population for a given gestational age at birth. *Small for gestational age* is defined as a birth weight below the 10th percentile for infants of the same gestational age.
  - v. *Perinatal mortality* is a binary indicator for whether there was a fetal death at or after 20 weeks of gestation or mortality within the first 7 days of life.

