## **A. Introduction**

During the first two years of the COVID-19 pandemic, the City of Chelsea, Massachusetts held a lottery to allocate cash benefits to its residents for ten months. In one of the original analyses of the Chelsea Eats program, the survey results showed that there was a higher rate of pregnancy in the treatment group compared to control. The underlying mechanism, however, remained unclear; the cash benefit could theoretically have induced changes in family planning or in maternal health, leading to the observed changes in pregnancy rates. Using data from the Chelsea Eats program, we propose to study the impact of the cash benefit on reproductive and perinatal health.

This proposal and analysis plan detail the intervention, randomization, and data source. Importantly, while this analysis plan is specified after the conduct of the trial, it does pre-specify the outcomes and statistical analysis prior to analysis of the data. No analyses of post-intervention outcomes were conducted prior to gaining access to the data.

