### *D.2. Planned Outcomes*

Outcomes will be assessed on a per-participant basis and measured using the electronic health record data.

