#### 1. Primary Outcome

##### a. Pregnancy

- i. We will first confirm the result from the survey data by assessing for pregnancies using the electronic health record data.
- ii. Pregnancies will be identified in the electronic health record as a positive urine or blood pregnancy test, ultrasound, and/or diagnosis codes over the 10 months of the trial.
- iii. We will then use the electronic health record identify live child births delivered vaginally or via Cesarean section. These can occur after the 10-month duration of trial.
- iv. Any pregnancy without an eventual delivery (not carried to term), the primary outcome for our main analysis, could be indicative of miscarriage, abortion, or fetal death, which will be assessed further with the secondary outcomes below.

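### Several prenatal-care and birth measures (D.2, secondary outcomes e and f) exist only for women with a pregnancy or birth, so E.2's intent-to-treat reading does not hold for them; for the rest of e and f the analysis set is not settled

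*Combined protocol and SAP*

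**What the plan says.** Section D.2, secondary outcome e, is "Number and timing of prenatal visits before delivery". It adds initiation in the first trimester and a plan to "calculate the Adequacy of Prenatal Care Utilization (APNCU) Index", a four-level classification. For outcome f, "we will construct a composite of at least one of: low birth weight, preterm birth, small for gestational age, or perinatal mortality", with birth weight, gestational age and birth weight for gestational age also defined as continuous measures. Neither item names an analysis set or says how a woman with no pregnancy or no birth is coded.

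The nearest general statements are these:

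- D.1 matches female participants of childbearing age to their health records.
- D.2 opens with "Outcomes will be assessed on a per-participant basis".
- E.2 applies one intent-to-treat linear model to all the D.2 outcomes and describes the weighted coefficient on winning the lottery as unbiased.
- E.5 gives the secondary outcomes adjusted p-values.

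Section A reports that in the earlier survey "there was a higher rate of pregnancy in the treatment group compared to control", and offers as explanation that "the cash benefit could theoretically have induced changes in family planning or in maternal health". D.2 item 1.a.iv describes the primary outcome as "Any pregnancy without an eventual delivery (not carried to term), the primary outcome for our main analysis".

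**The concern.** Randomization makes the arms comparable as randomized. It does not make the pregnant women in one arm comparable with the pregnant women in the other if the intervention influences who becomes pregnant or who delivers. The plan takes that influence seriously: it is the finding that motivates the study, and pregnancy without delivery is the main primary outcome. A measure available only after pregnancy or birth is therefore compared between groups that cash may itself have selected.

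Section A asks whether cash worked through family planning or through maternal health. Items e and f supply the prenatal-care and birth evidence on that question. A conditional difference presented as intent-to-treat could reflect only who conceived or delivered, or could hide a real effect. If women without a birth are coded 0, the comparison stays randomized, but the result also moves with the number of births and could be misread as birth health. The reader needs to know which version is reported.

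**Working it through.** **Step 1. Sort the items by whether a value exists without a pregnancy or birth.**

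| Item in D.2 | Value for a woman with no pregnancy or birth? | Consequence under E.2 |
|---|---|---|
| APNCU category | None of the four levels applies | Necessarily conditional |
| Timing of initiation | None | Necessarily conditional |
| Birth weight, gestational age, weight for gestational age | None | Necessarily conditional |
| Visit count, first-trimester indicator, birth composite | Could be coded 0 | Randomized if all matched women are included; conditional if restricted |

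**Step 2. Look for a repair elsewhere in the plan.** The lottery weights in E.2 correct for unequal numbers of tickets. Baseline covariates, and the E.1 balance checks on the final sample, deal only with observed characteristics. E.1 speaks of attrition, with death as its example, and not of selection through pregnancy. E.4 lists no sensitivity analysis for it.

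**Step 3. Illustrate the size.** The plan has no figure to reproduce. From section B: 3,615 households applied and 2,074 were chosen, leaving 3,615 − 2,074 = 1,541. Everything else is assumed: births in 6% of control and 8% of treated women; 15% composite risk in births that would occur in either arm; added births at 5%, 15% or 25% risk; no effect of cash on any individual birth.

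Treated risk among births = (6 × 15 + 2 × r) / 8:

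- r = 5: 100/8 = 12.5%, difference −2.5 points
- r = 15: 120/8 = 15.0%, difference 0
- r = 25: 140/8 = 17.5%, difference +2.5 points

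**Step 4. Allow for conceptions before the lottery.** Pregnancies are identified by tests, ultrasound or "diagnosis codes over the 10 months of the trial", so some will have been conceived earlier, and cash cannot have caused those conceptions. If they make up half of control births and the other half rises in the same ratio, treated births are 3 + 3 × (8/6) = 7%. Treated risk is then (90 + 5)/7 = 13.57% or (90 + 25)/7 = 16.43%, a difference of ±1.43 points.

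**Step 5. Compare with sampling error.** The number of matched women is not given. One matched woman per household would give 1,541 × 0.06 = 92.5 control and 2,074 × 0.08 = 165.9 treated births; other sizes scale this. SE = √[0.15 × 0.85 × (1/b_control + 1/b_treated)], unweighted and unclustered. Rejection rates are two-sided at nominal 5%, with arm-specific variances.

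| Scale | Births, control / treated | SE (points) | 2.5 / SE | Rejection, step 3 | Rejection, step 4 |
|---|---|---|---|---|---|
| 0.25 | 23.1 / 41.5 | 9.27 | 0.27 | 5.8–5.9% | 5.3% |
| 0.5 | 46.2 / 83.0 | 6.55 | 0.38 | 6.6–6.8% | 5.5% |
| 1 | 92.5 / 165.9 | 4.63 | 0.54 | 8.2–8.6% | 6.0–6.1% |
| 1.5 | 138.7 / 248.9 | 3.78 | 0.66 | 9.9–10.4% | 6.5–6.6% |

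The birth counts, SE and ratio are for step 3; in step 4 the treated births are 7/8 of those shown.

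**Step 6. The all-women version.** At equal risk, control is 6% × 15% = 0.90% and treated is 8% × 15% = 1.20%: a difference of 0.30 points from birth frequency alone. At scale 1 this gives z = 0.88 and rejection of 14.3%. That is a real difference per woman randomized, not a false positive, but it says nothing about risk per birth.

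**Step 7. Check the birth base.** D.2 item 1.a.iii defines deliveries as live births, and 1.a.iv lists fetal death under pregnancy without delivery. The composite in f nevertheless counts fetal death at or after 20 weeks. So the composite plus deliveries without it does not equal the delivery rate unless those fetal deaths enter the same base.

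**The case against.** The strongest reply is that D.1, the per-participant statement in D.2 and the intent-to-treat statement in E.2 together put every matched woman in the denominator. For the visit count, first-trimester indicator and composite this is a fair reading, and the comparison would then be randomized. A reader might infer that the plan has chosen a biased analysis for all of e and f; the documents do not support that. What they show for these three is an unsettled analysis set. The composite also follows a cited study that may define its own set, which cannot be checked here. The reply does not reach the APNCU category, timing or the continuous birth measures, because a per-participant unit cannot supply a value that does not exist.

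Second, the bias may be small. That stands. Every rate in the illustration is assumed, the larger rejection rates need at least one matched woman per applicant household, and weighting and clustering would probably enlarge the SE.

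Third, the all-women composite answers the maternal-health question poorly, since it moves with birth frequency. That also stands, and is why it must be shown beside the pregnancy and delivery rates and not read as birth health.

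Fourth, only secondary outcomes are affected. True; the primary outcome is untouched.

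**Conclusion.** The point holds in two parts. For the APNCU category, timing of initiation and the continuous birth measures, E.2's reading of its coefficient as an unbiased effect of winning the lottery does not hold, because those values exist only after an event that cash may have changed. For the visit count, first-trimester indicator and birth composite, the same problem arises only if they are restricted to pregnant or delivered women, and D.2 leaves that open.

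Size and direction cannot be derived from the documents. Under the assumed rates the spurious among-births difference is at most about 2.5 points either way, or about 1.4 if half of control births were conceived before the lottery, and 0 if added births carry the same risk. Nominal 5% tests then reject roughly 5% to 10% of the time. A reader might infer that these results would be badly misleading; the figures do not show that. The case rests on a randomized label that these comparisons have not earned, and on an analysis set still to be chosen in a plan meant to be fixed before the data are analyzed. The change should be made. Confidence is medium.

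**What to change.** In D.2 e and f:

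- State the analysis set for each item.
- For the E.2 intent-to-treat contrast, define two indicators over all randomized matched women: the birth composite, and delivery with first-trimester initiation. Code both 0 where there is no qualifying birth.
- Report them beside the pregnancy and delivery rates, stating that they mix birth frequency with risk per birth and do not isolate maternal or birth health.
- Keep APNCU, timing, visit number, the continuous birth measures and the among-births composite, labelled as conditional comparisons not protected by randomization.
- Name which version of each item enters the Benjamini-Hochberg family in E.5.
- State whether a fetal death at or after 20 weeks counts in the birth denominator. If a complement (births without the composite) is shown, use the same base.

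The cost is SAP wording and a few indicators from the same records. The downside is that all-women effects are on a smaller scale and move with the birth rate, and the conditional results carry a weaker claim.

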### D.3. Patient Characteristics

The data includes information on participants' household size, disability status, veteran status, work status, income, receipt of other benefits or assistance, and utilization/spending prior to randomization. These characteristics come from the lottery application form or electronic health records and are assessed prior to randomization. In the event that there are high levels of missingness for any key covariate (i.e., >2%), multiple imputation methods will be used.

## E. Statistical Analysis

### *E.1. Evaluation of randomization, balance, and attrition*

We will test for balance between treatment and control based upon observable baseline characteristics for the overall study population.

Because differential attrition correlated with treatment, for example due to death, could introduce bias into our results, we will also evaluate the attrition rate and assess for balance between treatment and control based upon both baseline characteristics for the final analytic sample (and attritors) and potential causes of attrition.

### *E.2. Statistical specification*

Our primary analytic approach is an analysis based on the intent-to-treat principle that compares outcomes for those randomized into the treatment group to those who were randomized into the control group. Specifically, we will estimate the following linear regression model:

$$y_i = \beta_0 + \beta_1 \text{CASH}_i + \beta_3 \mathbf{X}_i + \epsilon_i,$$

where  $y_i$  is the utilization or clinical outcome for individual or household  $i$ . See section D.2. for a list of our primary and secondary outcomes. “ $\text{CASH}_i$ ” is an indicator for whether individual  $i$  won the lottery and was thus randomized into the treatment group.  $\mathbf{X}_i$  is a vector of covariates, specifically patient characteristics, including baseline (pre-randomization) values of the outcome variable, which are not explicitly necessary since they should be unrelated to treatment status, but they may increase the precision of our estimates to the extent that they explain some of the variance in the outcome.

The coefficient on  $\text{CASH}_i$ ,  $\beta_1$ , is our main coefficient of interest; it provides the difference in means between the treatment groups and the control group. In addition to our primary specification above that corresponds to testing for a level shift, we will also include an interaction term between an indicator for time and treatment status to test for changes in slope.

As described in section C, a household could receive additional lottery tickets by meeting specific criteria. Observations will thus be weighted by the inverse probability of winning the lottery so that  $\beta_1$  is an unbiased estimate of the relationship between winning the lottery and the outcome. An alternative specification that includes indicators for number of lottery tickets is discussed below. Standard errors will be clustered at the household level and adjusted for heteroskedasticity.

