### **C. Randomization and Participant Eligibility**

Between July 27, 2020 and August 17, 2020, the City accepted applications for the Chelsea Eats cash assistance cards. Multilingual information about the cards was distributed to individuals using the city-run food distribution sites. Additionally, information and applications were disseminated to community-based organizations, food pantries, faith groups, health care organizations, and low- and moderate-income housing complexes. Direct outreach to residents by city staff occurred in multiple locations, including food pantry lines, COVID-19 testing lines, and social service agencies. Applications could be submitted online via the city's website or on paper by dropping them off or mailing them to City Hall. In practice, most applications were submitted by residents attending one of the various city or community partner food pantries, where city staff, equipped with tablets, assisted residents with the application.

Eligibility criteria included:

- Resident of Chelsea, Massachusetts
- Household income at or below 30% of the U.S. Department of Housing and Urban Development's Area Median Income

The lottery was a weighted lottery. Specifically, a household could receive additional lottery tickets by meeting any of the following criteria:

- No one in the household was currently working
- The household was not receiving unemployment insurance
- The household was not receiving food assistance (e.g., SNAP benefits)
- There was a disabled household member
- There was a household member over 65 years of age
- There was a household member who was a veteran
- There was a household member who was under 6 years of age
- There was a household member between the ages of 6 and 17

The total number of lottery tickets per application ranged from 1 to 8. Although it was the city's intention to restrict households to a single application, some households managed to enter the lottery with more than one application. In these cases, the household still received only a single Chelsea Eats card. Records for the duplicate applicants will be combined into a single record, summing the lottery tickets across the duplicate records to determine the household's overall probability of winning the lottery. We account for the differential probability of winning the lottery across households in the statistical analysis (see section E.2).

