#### *E.4. Alternative specifications and sensitivity analyses*

Our primary specification includes patient characteristics and baseline values of the outcome in the model to improve power as well as any chance imbalance between the study arms after randomization. As described in section E.1., we will compare covariates between the treatment and control groups, and we will explore whether our results are sensitive to inclusion of these covariates in the model. Importantly, our primary specification accounts for differential probability of winning the lottery using inverse probability weights. As an alternative approach, we will include the set of covariates that are correlated with treatment probability into the model, specifically indicators for number of lottery tickets. Finally, as a sensitivity check, we will also conduct our analyses on the subpopulation of participants with established primary care at one of the clinical sites of care.

To ensure our estimates are robust to method of estimation, we will also estimate generalized linear models assuming a negative binomial distribution for the count utilization outcomes and a generalized linear model with a Bournoulli distribution and logit link function for the binary outcomes. In a final robustness check, we will Winsorize the utilization measures to ensure that our estimates are not sensitive to outliers.

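### E.2 weights every observation by 1/P(win) and no section states a control weight; as written, the rule leaves ticket count tied to treatment and does not make β1 unbiased

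*Combined protocol and SAP*

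**What the plan says.** Section C describes a lottery in which the number of tickets (1 to 8 per application, summed over duplicates) rises with criteria such as nobody working, no benefits, disability, veteran status, a member over 65, or children under 6 or aged 6 to 17. It promises that "We account for the differential probability of winning the lottery across households in the statistical analysis" and refers to E.2 for the method.

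E.2 gives the method: "Observations will thus be weighted by the inverse probability of winning the lottery". It presents this as what makes β1 unbiased. Of the covariates X it says that they are ones "which are not explicitly necessary since they should be unrelated to treatment status".

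E.4 adds only that "our primary specification accounts for differential probability of winning the lottery using inverse probability weights". Its alternative model adjusts for covariates correlated with treatment probability, "specifically indicators for number of lottery tickets". On the covariates in X it says "we will explore whether our results are sensitive to inclusion of these covariates in the model".

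D.3 lists the characteristics as "household size, disability status, veteran status, work status, income, receipt of other benefits or assistance, and utilization/spending prior to randomization". It does not name child ages, the over-65 criterion or ticket count, although it does say "These characteristics come from the lottery application form or electronic health records", so they may be available. E.1 does not say whether the balance tests are weighted.

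**The concern.** Weighting by the inverse of the probability of winning is right for winners. For controls the matching weight is the inverse of the probability of not winning. E.2 applies the first to all observations, and neither Section C nor E.4 supplies the second. An analyst who follows E.2 to the letter keeps the confounding that the weight is meant to remove.

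The description of X then fails as well. Work, benefits, disability and veteran status are both ticket criteria and D.3 covariates, so under the literal weight they are related to treatment. X would be doing the confounding control that the plan assigns to the weight, and how well it does so depends on what X contains. Having a young child earns a ticket, is not named in D.3, and could plausibly relate to pregnancy outcomes.

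Nothing sets a different weight for the secondary outcomes or the subgroups. In the E.4 comparison without covariates, a shift caused by the weighting could be misread as chance imbalance.

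**Working it through.** **Inputs from the documents.** 3,615 households applied and 2,074 won (2,074/3,615 = 57.4%; 1,541 did not). Tickets run from 1 to 8 per application. There is no ticket distribution, weight value or outcome gradient, so the plan has no figure to reproduce.

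**Algebra (no assumptions).** Let f_k be the share of applicants with k tickets and p_k their probability of winning.

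- Weight 1/p_k for everyone: winners f_k·p_k·(1/p_k) = f_k; controls f_k·(1−p_k)·(1/p_k) = f_k(1−p_k)/p_k. Winner-to-control odds at k: p_k/(1−p_k), the same as unweighted.
- Weight 1/p_k for winners and 1/(1−p_k) for controls: f_k in both arms, odds 1 at every k.

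Under the first rule the control arm is tilted towards low ticket counts.

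**One worked ticket mix (assumed).** Take p_k = 1−exp(−λk), with λ solved to give 2,074 expected winners.

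| k | 1 | 2 | 3 | 4 | 5 | 6 | 7 | 8 |
|---|---|---|---|---|---|---|---|---|
| f_k | .03 | .10 | .20 | .25 | .20 | .13 | .06 | .03 |
| p_k | .192 | .347 | .472 | .573 | .655 | .721 | .774 | .818 |
| f_k(1−p_k)/p_k | .126 | .188 | .224 | .186 | .105 | .050 | .018 | .007 |

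Weighted mean tickets among winners: Σk·f_k = 4.27. Among controls: 2.92/0.904 = 3.23. The gap is 1.04 tickets; unweighted it is 4.65 − 3.75 = 0.90. If risk rises by 1 percentage point (pp) per ticket and the true effect is zero, the unadjusted bias is 1.04 × 1 = 1.04 pp. A simulated ticket-weighted draw without replacement (2,000 runs) gave 1.04 pp for the literal rule, 0.90 unweighted, −0.001 for arm-specific weights and 0.002 for ticket indicators (Monte Carlo standard errors about 0.02). Two other assumed mixes, uniform and low-skewed, gave literal gaps of 2.05 and 1.22 tickets against 1.88 and 1.34 unweighted. The literal rule can therefore enlarge or slightly shrink the gap, but does not remove it.

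**Bias with covariates (all assumed, zero true effect).** Tickets were built from the eight Section C criteria under four sets of prevalences and three degrees of correlation, giving 12 scenarios. The modelled D.3 set is work, unemployment insurance, food aid, disability, veteran status and household size. Income, prior utilization and baseline outcome were not modelled.

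| Assumed risk gradient | X | Bias, 1/p for all (pp) |
|---|---|---|
| +3 pp child under 6, +1 pp child 6–17 | none | +0.38 to +0.84 |
| same | modelled D.3 | +0.19 to +0.25 |
| same | D.3 + both child criteria | 0.00 |
| 1 pp per ticket | none | +0.60 to +1.31 |
| same | modelled D.3 | +0.13 to +0.17 |
| same | D.3 + both child criteria | +0.02 to +0.07 |
| −3 pp each for child 6–17 and member over 65 | modelled D.3 | −0.06 to −0.21 |

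Unweighted with the modelled D.3 set, the child and per-ticket gradients give +0.21 to +0.26 and +0.14 to +0.18, so most of the reduction comes from X. Arm-specific weights give 0.00. Adding the over-65 criterion to D.3 and the child criteria brings the per-ticket bias to about 0. Other ways of generating household size move the child-gradient figure with D.3 to between +0.10 and +0.29 pp.

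**Primary test.** 1,500 replicates, base risk 4%, 1,000 or 2,000 women, one per household, modelled D.3 set. With the modest child gradient the bias is 0.13 to 0.24 standard errors. Rejection of the nominal 5% test is 4.7% to 5.9% (arm-specific 4.9% to 5.5%). With a steep gradient of +12/+4 pp it is 8.1% to 11.6% (arm-specific 4.5% to 5.7%). Without X and with the modest gradient it is 7% to 11%.

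**Balance.** The winner-minus-control gap in the share of households with a child under 6 is 8.0 to 18.7 pp unweighted, 8.6 to 20.3 pp under 1/p for all, and 0 under arm-specific weights.

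**The case against.** The strongest reply is that this is a gap in wording. E.2 states the aim of unbiasedness and says covariates should be unrelated to treatment, and E.4 uses the standard name of the method. All three fit weights on the assignment actually received and do not fit 1/p for everyone. That reading is possible, and nothing here shows that a wrong analysis was run. But E.2 names the probability of winning, and the document presents itself as pre-specifying the analysis, so the estimator should not depend on the reader inferring a formula that is not written.

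Second, the consequence for the primary test is small under the modest gradient. The rejection ranges overlap, and the Monte Carlo standard error near 5% is √(0.05 × 0.95/1,500) = 0.56 points. Mean squared error barely changes: squared bias is 0.13² to 0.24² = 1.7% to 5.8% of the variance, while a 2% to 3% larger standard error adds about 4% to 6%. This stands.

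Third, the simulated covariate set is partial, and the planned X could lower the bias further. The steep gradient has no support in the documents; it puts a household with children of both ages at 4 + 12 + 4 = 20%, five times the base. Both points stand, so the magnitudes are illustrations.

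Fourth, the E.4 ticket-indicator model removes the bias under a constant effect and could expose a discrepancy. It is only an alternative, though; if E.2 is followed literally, the headline estimate still carries the bias.

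Finally, the documents do not say whether the 2,074 includes waitlisted households, which affects p. This also stands.

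**Conclusion.** The concern holds and should be fixed. That the literal weight leaves the winner-to-control odds unchanged at each ticket count is algebra and rests on no assumption. The unbiasedness claimed in E.2 therefore does not follow from the rule stated there. Bias arises only if ticket count is related to the outcome after adjustment for X.

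Its size and sign are not known from the documents. The ticket mix of matched women aged 15 to 44, the form of the draw and the outcome gradients are all assumed here. On those assumptions the threat to the primary test is small with D.3-type covariates and a modest gradient. It is larger for outcomes strongly tied to having young children and for the comparison without covariates. Confidence is medium, because arm-specific weights may have been intended.

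**What to change.** State in E.2:

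> Treatment observations are weighted by 1/p_i and control observations by 1/(1−p_i), where p_i is the probability, given the household's summed tickets, of ending in the treatment group by the initial draw or the waitlist.

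Add how p_i is obtained, and whether the 2,074 includes waitlisted households. Say that the E.1 balance tests use the same weights. Keep the ticket-indicator model in E.4 as the sensitivity analysis.

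The wording is short; deriving p_i is the real work. The documents do not describe the mechanics of the draw or say whether the waitlist was ticket-weighted, and summed duplicates can exceed 8 tickets. The existing E.2 rule needs a value of p as well.

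On the assumed scenarios with the modelled D.3 set, the standard error rises 2% to 3% over 1/p for all with the modest gradient and 8% to 11% with the steep one. Control weights reach 5.9 to 9.6 at 8 tickets, 14 to 30 at 12 and 35 to 91 at 16. If 5% of households had doubled tickets, the control-arm Kish design effect would move from 1.07–1.11 to 1.12–1.18 (1.11–1.14 under 1/p for all). The plan should therefore also say in advance how very large weights will be handled.
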